17.4 Secondary endpoints

The planned secondary endpoints will be analysed as outlined in this Section.

17.4.1 Supportive secondary endpoints

17.4.1.1 Efficacy endpoints

BMI SDS at 30 and 82 weeks

The change in BMI SDS from baseline to 30 and 82 weeks and from 56 weeks to 82 weeks will be analysed using the same statistical method as used for the main analysis of the primary endpoint.

BMI

The changes in BMI from baseline at 30 and 56 weeks will be analysed separately with the same type of ANCOVA with MI as used for the main analysis of the primary endpoint, but with the baseline BMI as covariate instead of the baseline BMI SDS. Change from 56 weeks to 82 weeks will be summarised using descriptive statistics.

In addition, the following categorical endpoints related to BMI will be evaluated:

- Percentage of subjects achieving $\geq 5\%$ reduction in baseline BMI at 30, 56 and 82 weeks
- Percentage of subjects achieving $\geq 10\%$ reduction in baseline BMI at 30, 56 and 82 weeks

These endpoints will be analysed separately using a logistic regression model. The response will be a binary outcome (yes/no) indicating for each subject whether the respective minimum reduction in BMI has been achieved. The model will include treatment, sex, region, baseline glycaemic category, stratification factor for Tanner stage and interaction between baseline glycaemic category and stratification factor for Tanner stage as fixed effects, and baseline BMI and baseline age as covariates. The results will be presented as odds ratios together with the associated 95% CIs.

For the analysis of the categorical endpoints, missing BMI values will be imputed using the 100 complete datasets from the MI performed for the corresponding analysis on the continuous change in BMI. The logistic regression will be performed on each of these datasets. Rubin's formula will then be applied on the 100 estimates of the log odds ratio and the associated SDs to produce a pooled estimate and SD. These pooled values will lastly be used to calculate the 95% CI for the odds ratio.

PRO outcome

The PRO questionnaire IWQOL-Kids will be evaluated similarly to the primary endpoint. That is, the change in PRO score from baseline at 30 and 56 weeks will be analysed separately using the same type of ANCOVA with MI as used for the main analysis of the primary endpoint, but with the corresponding baseline PRO score instead of the baseline BMI SDS as covariate.

Glycaemic category

The change in glycaemic category (normoglycaemia, pre-diabetes, T2DM) from baseline at 30 and 56 weeks and change from 56 weeks to 82 weeks will be summarised using descriptive statistics.

Furthermore, two separate analyses will be performed on the binary variable normoglycaemia (yes/no) at 30 and 56 weeks, using a logistic regression model with the factors treatment, sex, region, baseline glycaemic category, stratification factor for Tanner stage and interaction between baseline glycaemic category and stratification factor for Tanner stage, and baseline age as covariate. Missing data will be handled by an MI method similar to the one used for the main analysis of the primary endpoint, but adapted to the logistic regression model. The results will be presented as odds ratios together with the associated 95% CIs.

Other supportive secondary efficacy endpoints

The following other efficacy variables will be evaluated:

- Body weight
- Waist circumference
- Waist-to-hip circumference ratio
- Cardiovascular biomarker (hsCRP)

- Fasting lipids (TC, LDL-cholesterol, HDL-cholesterol, non-HDL cholesterol, VLDL cholesterol, TG and FFA)
- Systolic and diastolic blood pressure
- Quantitative glucose metabolism parameters (HbA_{1c}, FPG, fasting insulin, fasting C-peptide, HOMA-B^a and HOMA-IR^a)

The changes in these variables from baseline at 30 and 56 weeks will be analysed using the same type of ANCOVA with MI as used for the main analysis of the primary endpoint, but with the baseline value of the corresponding variable instead of the baseline BMI SDS as covariate. Each endpoint will be analysed separately. For hsCRP, fasting lipids, fasting insulin, fasting C-peptide, HOMA-B and HOMA-IR, the response and baseline values will be log transformed prior to the analysis. The change in these variables from 56 weeks to 82 weeks will be summarised using descriptive statistics.

^a The calculation of the HOMA endpoints will be done as follows:

- Beta-cell function (%) = $20 \cdot \text{fasting insulin}[\text{mU/L}] / (\text{FPG}[\text{mmol/L}] - 3.5)$
- Insulin resistance (%) = $\text{fasting insulin} [\text{mU/L}] \cdot \text{FPG} [\text{mmol/L}] / 22.5$.

17.4.1.2 Safety endpoints

Adverse events

AEs will be summarised for the safety analysis set separately for three periods:

- Run-in period: defined as events with onset date between V2 (included) and the first day of trial product administration (not included).
- In-trial period: defined as events with onset date between the first day of trial product administration and the last study visit.
- On-treatment period: defined as events with onset date between the first day of trial product administration and whatever comes first: a) 14 days after the last day on trial product , b) follow-up visit (V26 for subjects with trial product discontinued), or c) last study visit (subjects withdrawn without follow-up visit).

A treatment-emergent adverse event (TEAE) is defined as an event that occurs in the “on-treatment” period.

The AEs will be coded using the most recent version of the Medical Dictionary for Regulatory Activities (MedDRA). They will be presented in terms of the number and percentage of subjects with at least one event, the number of events and the event rate per 1000 years. AEs in the screening period (prior to randomisation) will be presented in listings.

Hypoglycaemic episodes

Hypoglycaemic episodes will be summarised descriptively by severity and treatment in terms of the number and percentage of subjects with at least one episode and the total number of episodes. Separate summaries will be made by severity (the ISPAD criterion for severe hypoglycaemia⁴⁹). In

the same way as for AEs, there will be separate summaries for the “in-trial” and “on-treatment” periods. Hypoglycaemic episodes in the screening period will be presented in listings.

Classification of Hypoglycaemia

Treatment emergent: hypoglycaemic episodes will be defined as treatment emergent if the onset of the episode occurs on or after the first day of trial product administration, and no later than 14 days after the last day on trial product.

Nocturnal hypoglycaemic episodes: are episodes occurring between 23:00 and 07:00 both inclusive.

[figure not shown]
Hypoglycaemic episodes are classified according to ISPAD’s definition of severe hypoglycaemia⁴⁹ as well as the Novo Nordisk classification of hypoglycaemia; see [Figure 17–1](#) and the ADA classification of hypoglycaemia; see [Figure 17–2](#)).

Novo Nordisk classification of hypoglycaemia in paediatrics

In normal physiology, symptoms of hypoglycaemia occur below a plasma glucose level of 3.1 mmol/L (56 mg/dL)⁵⁸. Therefore, Novo Nordisk has included hypoglycaemia with plasma glucose levels below this cut-off point in the definition of BG-confirmed hypoglycaemia.

Novo Nordisk uses the following classification (see [Figure 17–1](#)) in addition to the ADA classification:

- Severe hypoglycaemia according to the ISPAD classification⁴⁹: Was the hypoglycaemic episode associated with severe neuroglycopenia, usually resulting in coma or seizure and requiring parenteral therapy (glucagon or intravenous glucose)?
- Symptomatic BG-confirmed hypoglycaemia: An episode that is BG-confirmed by plasma glucose value < 3.1 mmol/L (56 mg/dL) **with** symptoms consistent with hypoglycaemia.
- Asymptomatic BG-confirmed hypoglycaemia: An episode that is BG-confirmed by plasma glucose value < 3.1 mmol/L (56 mg/dL) **without** symptoms consistent with hypoglycaemia.
- Severe or BG-confirmed symptomatic hypoglycaemia: An episode that is severe according to the ISPAD classification⁴⁹ or BG-confirmed by a plasma glucose value <3.1 mmol/L (56 mg/dL) with symptoms consistent **with** hypoglycaemia.
- BG-confirmed hypoglycaemia: An episode that is BG-confirmed by a plasma glucose value < 3.1 mmol/L (56 mg/dL) **with** or **without** symptoms consistent with hypoglycaemia.
- Severe or BG-confirmed hypoglycaemia: An episode that is severe according to the ISPAD classification⁴⁹ or BG-confirmed by a plasma glucose value <3.1 mmol/L (56 mg/dL) **with** or **without** symptoms consistent with hypoglycaemia.

[figure not shown]
Note: Glucose measurements are performed with capillary blood calibrated to plasma equivalent glucose values

BG: blood glucose PG: plasma glucose SMPG: Self-measured plasma glucose

Figure 17–1 Novo Nordisk classification of hypoglycaemia in paediatric subjects

ADA/ISPAD classification of hypoglycaemia in paediatric subjects^{48, 49}

- Severe hypoglycaemia according to the ISPAD classification⁴⁹: Was the hypoglycaemic episode associated with severe neuroglycopenia, usually resulting in coma or seizure and requiring parenteral therapy (glucagon or intravenous glucose)?
- Asymptomatic hypoglycaemia: An episode not accompanied by typical symptoms of hypoglycaemia, but with a measured plasma glucose concentration ≤ 3.9 mmol/L (70 mg/dL).
- Documented symptomatic hypoglycaemia: An episode during which typical symptoms of hypoglycaemia are accompanied by a measured plasma glucose concentration ≤ 3.9 mmol/L (70 mg/dL).
- Pseudo-hypoglycaemia: An episode during which the person with diabetes reports any of the typical symptoms of hypoglycaemia with a measured plasma glucose concentration > 3.9 mmol/L (70 mg/dL) but approaching that level.
- Probable symptomatic hypoglycaemia: An episode during which symptoms of hypoglycaemia are not accompanied by a plasma glucose determination but that was presumably caused by a plasma glucose concentration ≤ 3.9 mmol/L (70 mg/dL).

Note: Glucose measurements are performed with capillary blood calibrated to plasma equivalent glucose values

PG: plasma glucose SMPG: Self-measured plasma glucose

Figure 17–2 ADA/ISPAD classification of hypoglycaemia in paediatrics

Anti-liraglutide antibodies

Anti-liraglutide antibodies will be summarised in terms of the number and percentage of subjects per visit that are antibody-positive, antibody-negative, cross-reacting and in vitro neutralising.

In addition, a comparison of the change in HbA_{1c} and body weight between antibody-positive and antibody-negative subjects will be performed using descriptive statistics and graphs. Listings with the individual antibody results will also contain information about the HbA_{1c} levels and body weight measurements. The impact of anti-liraglutide antibodies on safety will be similarly assessed by descriptive comparisons between antibody-positive and antibody-negative subjects.

Bone age assessment

Bone age assessment at baseline and change in bone age assessment will be summarised using descriptive statistics.

ECCG

Summary statistics and the frequencies of shifts from baseline at 30 and 56 weeks will be tabulated for each treatment group.

Pulse

Summary statistics and the frequencies of shifts from baseline to 30 and 56 weeks and from 56 weeks to 82 weeks will be tabulated for each treatment group. In addition, statistical analyses similar to those made for blood pressure will be performed for change from baseline to 30 and 56 weeks.

Laboratory parameters

Summary statistics will be tabulated for each laboratory parameter. The distributions will also be presented graphically using box plots by treatment and week.

For each laboratory parameter, the values will be compared to the relevant reference ranges. The results will be presented as follows:

- Shifts from baseline at 30 and 56 weeks and from 56 weeks to 82 weeks will be tabulated. The shift tables will include the number of subjects below, within and above the reference range at each visit
- The proportion of subjects with laboratory values outside the reference range will be tabulated per visit and treatment group
- Individual values outside the reference range (abnormal values) will be listed by treatment and subject

Pubertal status

Tanner stage at screening as well as changes in Tanner stage at 30 and 56 weeks and change from 56 weeks to 82 weeks, will be summarised using descriptive statistics.

Physical examination

Physical examination at screening and changes in physical examination will be summarised.

Height SDS

Height SDS⁵⁹ at screening and changes in height SDS will be summarised.

Mental health questionnaires

Results from the mental health questionnaires PHQ-9 and C-SSRS will be summarised using descriptive statistics and the frequencies of shifts from baseline to 30 and 56 weeks and from 56 weeks to 82 weeks will be tabulated for each treatment group.

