8.1.9 Withdrawal from trial

If a subject and/or the subject's LAR(s) withdraw consent, the investigator must aim to undertake procedures similar to those for the end of treatment (V25) as soon as possible, and a follow-up visit (V26) two weeks later.

If a subject and/or the subjects LAR(s) withdraw consent after end of treatment (V25), the investigator must aim to undertake procedures similar to those for the end of trial (V30) as soon as possible.

The end of trial form must be completed and final drug accountability must be performed even if the subject is not able to come to the trial site. A treatment discontinuation session must be made in IWRS. The case book must be signed.

Although a subject is not obliged to give his/her reason(s) for withdrawing consent, the investigator must make a reasonable effort to ascertain the reason(s), while fully respecting the subject's rights. Where the reasons are obtained, the primary reason for withdrawing consent must be specified on the end-of-trial form in the eCRF.

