12.2 Reporting of adverse events

All events meeting the definition of an AE must be collected and reported. This includes events from the first trial-related activity after the subject has signed the informed consent until the end of the post-treatment follow-up period (week 82). The events must be recorded in the applicable eCRF forms in a timely manner; see timelines below and [Figure 12-1](#).

During each contact with the trial site staff, the subject must be asked about AEs and technical complaints, for example by asking: “Have you experienced any problems since the last contact?”

All AEs, either observed by the investigator or subject, must be reported by the investigator and evaluated.

All AEs must be recorded by the investigator on an AE form. The investigator should report the diagnosis, if available. If no diagnosis is available, the investigator should record each sign and symptom as individual AEs using separate AE forms.

For SAEs, a safety information form must be completed in addition to the AE form. If several symptoms or diagnoses occur as part of the same clinical picture, one safety information form can be used to describe all the SAEs.

For all non-serious AEs, the applicable forms should be signed when the event is resolved or at the end of the trial at the latest.

Timelines for initial reporting of AEs:

[figure not shown]
The investigator must complete the following forms in the eCRF within the specified timelines:

SAEs: The AE form **within 24 hours** and the safety information form **within 5 calendar** days of the investigator's first knowledge of the SAE. Both forms must be signed within 7 calendar days from the date the information was entered in the eCRF.

For SAEs requiring reporting on a specific event form: In addition to the above the specific event form within **14 calendar days** from the investigator's first knowledge of the AE.

If the eCRF is unavailable, the concerned AE information must be reported on a paper AE form and sent to Novo Nordisk by fax, e-mail or courier within the same timelines as stated above. When the eCRF becomes available again, the investigator must enter the information on the form into the eCRF. See Section [13](#).

Contact details (fax, telephone, e-mail and address) are provided in the investigator trial master file.

Timelines are for the completion of forms from the time of investigator's awareness

AEs requiring specific event forms are described in Section 12.1.4 and 12.1.5

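### AE summary periods end at the last study visit, so a known AE that starts after it in a subject who withdraws and never returns is in neither post-baseline period and is not a TEAE

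*Protocol*

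**What the plan says.** Protocol 17.4.1.2 summarises AEs in three periods: run-in, in-trial and on-treatment.

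- **In-trial:** "In-trial period: defined as events with onset date between the first day of trial product administration and the last study visit". There is no clause for death, loss to follow-up or contact without a visit.
- **On-treatment:** starts at first dose and ends at the earliest of "a) 14 days after the last day on trial product", "b) follow-up visit (V26 for subjects with trial product discontinued") and "c) last study visit (subjects withdrawn without follow-up visit").
- **TEAE:** "A treatment-emergent adverse event (TEAE) is defined as an event that occurs in the" on-treatment period.
- **Treatment-emergent hypoglycaemia**, same section: onset "no later than 14 days after the last day on trial product", with no visit cut.

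Protocol 12.2 requires AEs to be collected "until the end of the post-treatment follow-up period (week 82") and asked about at every contact, not only at visits. Protocol 6.5 counts a subject as withdrawn only if the subject or the legal representative declines any further contact. Protocol 8.1.9 and 8.1.10 ask sites to aim for a V25-type visit as soon as possible after withdrawal or drug discontinuation, and V26 two weeks later. SAP 2.4.1.2 lists the safety endpoints. SAP 3.3 alters the AE outputs for the run-in period only. Neither redefines the in-trial or on-treatment end dates.

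**The concern.** A subject can go on injecting after the last attended visit, have an AE, and leave without another visit. The event may well be known: 8.1.9 has the site seek the reason for withdrawal, and 12.2 has it recorded. Yet the period rules give it no place in the post-baseline summaries, although the drug was being taken at onset.

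The number of TEAEs is one of the secondary endpoints selected for public disclosure (Protocol 4.2.2.2), and the in-trial table is the only other post-baseline AE summary. AEs that end participation are among those a safety comparison most needs. Protocol 8.1.9 also foresees such subjects, since "final drug accountability must be performed even if the subject is not able to come to the trial site".

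**Working it through.** The plan states no figure to reproduce, so the check applies the rules to cases.

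**Inputs.** Last attended visit on day 85 (V15 in SAP Table 3-1). Last dose and AE onset both on day 100 (assumed for illustration). The last study visit is read as the last one attended.

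**Rules.** In-trial end = last attended visit. On-treatment end = min(last dose + 14, V26 if held, last visit if withdrawn without a follow-up visit). Last dose + 14 = day 114.

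| Case | In-trial end | On-treatment end | In-trial? | TEAE? |
|---|---|---|---|---|
| Stops drug; V25-type visit day 107, V26 day 121, x-visits to day 575 | 575 | min(114, 121) = 114 | yes | yes |
| Withdraws; V25-type visit day 107, V26 day 121 | 121 | min(114, 121) = 114 | yes | yes |
| Withdraws; V25-type visit day 107 only | 107 | min(114, 107) = 107 | yes | yes |
| Withdraws; no later visit | 85 | min(114, 85) = 85 | **no** | **no** |
| Dies; death not classed as withdrawal | 85 | 114 | **no** | yes |
| Dies; death classed as withdrawal | 85 | min(114, 85) = 85 | **no** | **no** |

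Under the hypoglycaemia rule the cut-off is day 114 in all six cases, so day 100 is always treatment-emergent. Hypoglycaemic episodes are also to be tabulated by the in-trial and on-treatment periods. The same episode can then be treatment-emergent by its own definition but not on-treatment.

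In the fifth row the event is on-treatment but not in-trial, so the one period is no longer contained in the other.

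**Length of window lost under option c).** Scheduled visits on treatment are 1 week apart up to week 4, then 4 or 5 weeks apart: 7 to 35 days. The loss runs from the last visit to last dose + 14, so at most about 7 + 14 = 21 days early on and 35 + 14 = 49 days at the longest gap.

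**Share of such AEs lost (illustration).** Assume the last dose falls uniformly between visits I days apart and the AE starts L days before the last dose. The share starting after the last visit is max(0, 1 − L/I).

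| I (days) | L = 3 | L = 7 | L = 14 |
|---|---|---|---|
| 7 | 57% | 0% | 0% |
| 28 | 89% | 75% | 50% |
| 35 | 91% | 80% | 60% |

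These shares apply only to subjects who never return.

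**Upper bound on subjects.** Protocol 17.1 assumes 40% withdrawal at week 56: 0.40 × 228 = 91.2, about 91. Anyone who attends a follow-up visit is not subject to option c), so the true number is lower by an unknown amount.

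**The case against.** The strongest reply is that the usual case is already covered. Subjects who stop drug or withdraw are to be called in, and an AE followed by that visit stays in both periods, as the first three rows show. This stands, and it limits the point to subjects with no later visit.

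A reader might infer that every death after the last visit drops out of the TEAE count. The documents do not support that. Option c) applies to withdrawn subjects, and 6.5 ties withdrawal to declining contact. On that text, a fatal event with onset within 14 days of the last dose is a TEAE under option a) and is missing only from the in-trial table. The same holds for a subject who refuses visits but still takes calls. A death many weeks after the last dose, say between V26 and the next x-visit, is not treatment-emergent under any rule; only its in-trial status is at issue.

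If the last study visit meant the scheduled week 82 visit, the in-trial gap would close, but option c) would then serve no purpose.

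It is also fair that SAP 2.4.1.2 plans descriptive safety summaries unless otherwise stated, that serious events are reported individually within 24 hours, and that the data monitoring committee sees unblinded data. The defect is in the comparative tables, not in the detection of individual serious cases. Finally, the most frequent AEs, nausea and diarrhoea, start in weeks 1 to 4 (Protocol 18.1), when visits are weekly and the gap is shortest.

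**Conclusion.** The point holds in a limited form. For a subject who withdraws between visits and attends no later visit, any known AE with onset after the last attended visit is in neither post-baseline period and is not a TEAE. A fatal event starting after the last visit is outside the in-trial period, and its TEAE status turns on an unstated classification of death. The AE and hypoglycaemia rules in 17.4.1.2 disagree, and the SAP does not reconcile them.

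The size is unknown. About 91 subjects is a ceiling that rests on the 40% planning assumption; the documents give no share who leave without any further visit. It may be tempting to conclude that the rule favours liraglutide, because gastrointestinal AEs are the most frequent on that drug. The documents give no AE-driven withdrawal by arm, so the direction of any bias is not established. The conclusion also rests on reading the last study visit as the last one attended.

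**What to change.** Add a change entry to SAP 3.3:

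- End the in-trial period at the latest of last study visit, last recorded contact, withdrawal date or death.
- End the on-treatment period at the last day on trial product plus 14 days, or at death if earlier. Delete option c), as the hypoglycaemia rule already does without it, and state explicitly whether option b) (V26) is kept.
- If the last dose date is unknown, use the last recorded contact date, after confirming that the eCRF captures it. Dose changes and the end-of-trial form are already recorded (Protocol 8.1.8.3 and 8.1.9), but no last-contact date is named there.
- Use the same end dates for the exposure time in the event rates, whose denominator 17.4.1.2 does not define.

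The cost is a few sentences and a little programming. AE counts may be slightly less favourable. AE ascertainment after the last visit is less complete than at visits, so the added exposure time is less fully observed, and the report should say so.

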12.3 Follow-up of adverse events

The investigator must record follow-up information by updating the forms in the eCRF. Follow-up information must be reported to Novo Nordisk according to the following:

- **SAEs:** All SAEs must be followed until the outcome of the event is “recovered/resolved”, “recovered/resolved with sequelae” or “fatal”, and until all queries have been resolved. Cases of chronic conditions, cancer or AEs ongoing at time of death (where death is due to another AE) may be closed with the outcome “recovering/resolving” or “not recovered/not resolved”. Cases can be closed with the outcome of “recovering/resolving” when the subject has completed the follow-up period and is expected by the investigator to recover.

The SAE follow-up information should only include new (e.g., corrections or additional) information and must be reported **within 24 hours** of the investigator’s first knowledge of the information. This is also the case for previously non-serious AEs which subsequently become SAEs.

- **Non-serious AEs:** Non-serious AEs must be followed until the outcome of the event is “recovering/resolving”, “recovered/resolved” or “recovered/resolved with sequelae” or until the end of the follow-up period stated in the protocol, whichever comes first, and until all queries related to these AEs have been resolved. Cases of chronic conditions, cancer or AEs ongoing at time of death (where death is due to another AE) may be closed with the outcome “recovering/resolving” or “not recovered/not resolved”. Cases can be closed with the outcome

of “recovering/resolving” when the subject has completed the follow-up period and is expected by the investigator to recover.

The investigator must ensure that the recording of the worst case severity and seriousness of an event is kept throughout the trial. A worsening of an unresolved AE must be reported as follow up with re-assessment of severity and/or seriousness of the event.

Queries or follow-up requests from Novo Nordisk must be responded to **within 14 calendar days** from the date of receipt of the request, unless otherwise specified in the follow-up request.

SAEs after end of trial: If the investigator becomes aware of an SAE with a suspected causal relationship to the investigational medicinal product occurring to a subject after the subject has ended the trial, the investigator should report this SAE within the same timelines as for SAEs during the trial.

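### TEAEs are defined by onset date alone, so an AE that starts in the run-in and worsens or becomes serious on treatment is counted neither as a TEAE nor as an in-trial AE

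*Protocol*

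**What the plan says.** **Collection.** Protocol 12.2 starts AE collection well before dosing: "This includes events from the first trial-related activity after the subject has signed the informed consent". The flowchart puts V2 at week -14 and randomisation, with the first dose, at week 0.

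**Allocation to periods.** Protocol 17.4.1.2 uses onset date for all three periods. The run-in period takes onsets from V2 up to, but not including, the first dosing day. The other two are "In-trial period: defined as events with onset date between the first day of trial product administration and the last study visit" and "On-treatment period: defined as events with onset date between the first day of trial product administration and whatever comes first" of three possible end points. The definition of interest then follows: "A treatment-emergent adverse event (TEAE) is defined as an event that occurs in the" on-treatment period. No clause mentions severity, seriousness or worsening.

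**Recording of worsening.** Protocol 12.3 says "A worsening of an unresolved AE must be reported as follow up with re-assessment of severity and/or seriousness of the event". Follow-up is entered by updating the existing eCRF forms, and the worst severity and seriousness are kept on the record. A non-serious event that turns serious is treated as follow-up information, due within 24 hours: "This is also the case for previously non-serious AEs which subsequently become SAEs".

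**Concomitant illness.** Protocol 8.2.2 and 12.1.1 make clinically significant worsening of a concomitant illness an AE in its own right. Section 8.2.2 limits that term to illness present at screening or found through a trial procedure before exposure.

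**SAP.** Section 2.4.1.2 lists the number of TEAEs without defining them. Section 3.3 changes only who enters the run-in AE outputs: everyone with at least one run-in visit.

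**The concern.** Each rule is ordinary on its own. Together they send one kind of on-treatment change to the wrong table. An AE that begins in the run-in and gets worse after first dose gains no new onset date, so the period rule keeps it in the run-in.

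Protocol 4.2.2.2 marks the number of TEAEs with an asterisk as a key endpoint for disclosure, and comparing safety between arms is a secondary objective. If liraglutide aggravates complaints that are already under way, that aggravation is missing from the summaries meant to show it. Protocol 18.1 names gastrointestinal events as the most frequent AEs with liraglutide 3.0 mg, and an ongoing complaint of that kind could plausibly be affected. Severe and serious events matter most, because their counts are small and one or two cases can change a table.

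**Working it through.** The plan gives no figure to reproduce. The check follows two hypothetical headaches through the rules. Both are mild before first dose and become severe at week 3 on trial product; they differ only in when they began.

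| Step | Present at V2 (week -14) | Starts spontaneously at week -4 |
|---|---|---|
| Recorded before first dose as | Concomitant illness (8.2.2) | AE, mild (12.2) |
| Becomes severe at week 3 | New AE (8.2.2, 12.1.1) | Follow-up on the existing AE (12.3) |
| Onset date available to the analysis | Week 3 | Week -4 |
| Severity on the record | Severe | Severe (worst case kept, 12.3) |
| Run-in summary (17.4.1.2) | No | Yes |
| In-trial summary (17.4.1.2) | Yes | No |
| TEAE (17.4.1.2) | Yes | No |

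The same on-treatment change is a TEAE in one column and a run-in event in the other. Nothing in either document gives a reason for the difference. If the second event became serious instead, 12.3 would again update the existing record and the last three rows would not change.

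The second column is not an empty class: 17.4.1.2 defines a run-in AE period, so the plan expects AEs that are not concomitant illness before first dose.

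**Effect on the comparison.** Let n be the number per arm (228/2 = 114), p the proportion entering treatment with an unresolved run-in AE, and qL and qP the proportions of these that worsen on liraglutide and on placebo. Randomisation follows the run-in, so p is the same in both arms in expectation. Then:

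- worsenings missing from the liraglutide arm: n × p × qL
- worsenings missing from the placebo arm: n × p × qP
- net loss from the between-arm difference: n × p × (qL − qP)

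The net loss is zero if qL = qP, and positive only if treatment itself worsens ongoing AEs. The documents give none of p, qL or qP, so neither the gross nor the net count can be derived.

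**The case against.** The strongest reply is that the gap is narrow and the events are not hidden. Most of this stands.

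- **Scope.** A reader might infer that any drug effect on an ongoing complaint drops out of the TEAE count. The documents do not support that. Worsening of anything present at screening, or found by a trial procedure before exposure, is already a new AE. Protocol 8.3.2, 8.4.3, 8.4.4 and 8.4.6 also require worsening in blood pressure, pulse, ECG and physical examination after screening to be reported as AEs. What remains is the AE that arises spontaneously in the run-in and is still open at first dose.
- **Oversight.** A reader might infer that an on-treatment SAE could vanish. It cannot: 24-hour reporting applies (12.3), the DMC reviews unblinded safety data (12.7.2, 18.1), and the event appears in the run-in outputs. Mood has its own route through repeated PHQ-9 and C-SSRS assessments. The run-in outputs are still a poor place to see a drug effect, because SAP 3.3 opens them to everyone with a run-in visit, which can include subjects never randomised.
- **Size.** A reader might attach a number. Assuming p of 10–30% and qL of 10–20%, the liraglutide arm would lose 114 × 0.10 × 0.10 = 1.1 to 114 × 0.30 × 0.20 = 6.8 worsenings. Those rates have no source in the documents. The result is also a gross count in one arm, whereas the bias depends on qL − qP and could be near zero.
- **Inference.** Section 12.3 does not say in terms that the onset date is kept. That is the natural reading of updating an existing form, but a data-entry guideline that is not among the documents could say otherwise.

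None of this supplies the missing clause. The in-trial summary does not recover the event, since it also uses onset date, and the SAP leaves the rule as it is.

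**Conclusion.** The point holds as a limited error in a definition. Following the plan as written, an AE that starts spontaneously in the run-in, is unresolved at first dose and then worsens or becomes serious on treatment is summarised as a run-in event carrying its worst on-treatment severity and seriousness. It is absent from both the TEAE and the in-trial summaries.

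This rests on reading 12.3 as leaving the onset date unchanged. The number of events is unknown. The documents do not support a claim that the safety comparison is biased by any stated amount, or that it must be biased at all. The direction would be toward no difference if liraglutide worsens ongoing AEs more than placebo does. The effect on the total TEAE count is probably small; its importance lies in severe and serious events. The case for acting is that the rule misclassifies events in an endpoint selected for disclosure and is cheap to correct.

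**What to change.** 1. In Protocol 17.4.1.2 and SAP 2.4.1.2, define a TEAE as an AE with onset in the on-treatment period, or an AE with onset before first dose that increases in severity or becomes serious during that period.
2. Apply the same rule to the in-trial summary, using the in-trial period.
3. Add to the AE form the date on which the event worsened or became serious. The new definition cannot be applied without it: the audit trail in 13.1 gives the date of data entry, not of worsening.

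Leave the follow-up rules in 12.3 otherwise unchanged. Closing the run-in record and opening a new AE at worsening would conflict with its requirements to report worsening as follow-up, to keep the worst severity and seriousness, and to follow non-serious AEs to outcome or the end of follow-up.

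The cost is one extra eCRF field, short wording changes in the two documents, and a few more TEAEs in the tables.
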